7.57 ExacTrac or PAIS will be used for image guidance

7.58 Plan deviations

	Deviation	
	Minor	Major
Target volumes	CTV_high D95% between 90% and 95%	CTV_high D95% <90%
Volume	CTV or PTV margins larger than allowed in the protocol	Contoured GTV does not include imaging-visible tumor
Organs at Risk	Will be assessed at the time of data review	Will be assessed at the time of data review

7.6 Concurrent chemotherapy

Concurrent chemotherapy will not be required by the protocol. However, retrospective data of Mayo Clinic patients receiving reirradiation revealed a significantly lower risk of radionecrosis when bevacizumab was administered concurrently. Thus, we recommend use of concurrent bevacizumab with radiotherapy when possible.

7.7 Follow-up protocol

7.71 Follow-up imaging

Once radiation treatment planning is complete, additional F-DOPA-PET scans will not be required. Standard of care MRI scans will be used for follow-up imaging.

7.8 Response assessment

Post-treatment tumor recurrence will be monitored with follow-up MRI imaging to assess tumor response based on RANO Working Group criteria until progression or death (or up to 2 years)

7.9 Patterns of failure

For patients who recur, follow-up imaging at progression will be co-registered with pre-treatment imaging in MIM Maestro™ and patterns of failure will be analyzed in the Eclipse treatment planning software (Varian Medical Systems, Palo Alto, CA) by determining the portion of recurrence volume (RecVol) that falls within the 95% isodose line of the PTV from the reirradiation plan.

7.91 Failures will be documented as 'central' relative to the treatment volume if >95% of the recurrence volume is within the 95% isodose line, 'in field' (80-95%), 'marginal' (20-80%), or 'distant' (<20%).

7.92 Failures will be documented as 'central' relative to the T1-CE MRI if >95% of the recurrence volume is within the T1-CE volume, 'in field' (80-95%), 'marginal' (20-80%), or 'distant' (<20%).

7.93 Failures will be documented as 'central' relative to the F-DOPA-PET avidity if >95% of the recurrence volume is within the PET volume (defined as T/N > 2.0), 'in field' (80-95%), 'marginal' (20-80%), or 'distant' (<20%).

7.931 Exploratory analysis for T2 FLAIR volumes, other T/N thresholds and SUV levels and their relationship with sites of failure will be investigated

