#### 1.6 Reirradiation is often used for treatment of progression:

Repeat courses of radiotherapy are often considered for progressive disease refractory to systemic therapy. Conventionally fractionated doses between 36 and 46 Gy have been used with minimal neurologic toxicity.[21-23] Hypofractionated doses of 24-50 Gy in 3.5-5 Gy fractions have also been used with minimal toxicity when limiting doses to <40 Gy.[22, 24-29] Mayer and colleagues proposed a cumulative normal tissue dose limit (2 Gy per fraction equivalent) of <100 Gy to limit the risk of radionecrosis.[30] In general, the target volume includes a minimal expansion beyond MRI contrast enhancement.[21, 24-27, 29] Median survival after reirradiation ranges from 7 to 10 months.[21-27, 29] The best outcomes are seen when more time elapses between primary radiation and reirradiation and in patients with lower-grade histology.[24-26, 31] In an analysis of patterns of recurrence after reirradiation, 60-70% recurrences were located in-field with the remainder located out of field.[25, 32] Thus, MRI contrast enhancement may not accurately reflect tumor location potentially resulting in imprecise targeting of radiation target volumes.

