###### 11.412 Partial Response (PR): Requires all of the following:

- $\geq 50\%$  decrease compared to baseline in the sum of products of perpendicular diameters of all measurable enhancing lesions sustained for at least 4 weeks
- No progression of non-measurable disease
- No new lesions
- Stable or improved non-enhancing (T2/FLAIR) lesions on same or lower dose of corticosteroids compared to baseline scan
- The corticosteroid dose at the time of the scan evaluation should be no greater than the dose at time of the baseline scan
- Stable or improved clinically

11.413 Stable Disease (SD): Requires all of the following:

- Does not qualify for complete response, partial response, or progression
- Minimum 4 weeks duration
- Stable non-enhancing (T2/FLAIR) lesions on same or lower dose of corticosteroids compared to baseline scan. In the event that the corticosteroid dose has been increased, the last scan considered to show stable disease will be the scan obtained when the corticosteroid dose was equivalent to the baseline dose
- Stable clinically

11.414 Progression: Defined by any of the following:

- $\geq 25\%$  increase in the sum of products of perpendicular diameters of enhancing lesions compared to the smallest tumor measurement obtained either at baseline (if no decrease) or best response, on stable or increasing doses of corticosteroids
- Significant increase in T2/FLAIR non-enhancing lesion on stable or increasing doses of corticosteroids compared to baseline scan or best response following initiation of therapy, not due to co-morbid events (e.g. radiation therapy, demyelination, ischemic injury, infection, seizures, post-operative changes, or other treatment effects)
- Any new lesion
- Clear clinical deterioration not attributable to other causes apart from the tumor (e.g. seizures, medication side effects, complications of therapy, cerebrovascular events, infection, etc.) or changes in corticosteroid dose. The definition of clinical deterioration is left to the discretion of the investigator but it is recommended that a decrease in 20% of KPS or from any baseline to 50% or less be considered, unless attributable to co-morbid events.
- Failure to return for evaluation due to death or deteriorating condition
- Clear progression of non-measurable disease

11.415 Pseudoprogression (PsP): All of the following must be true:

- Progression of contrast enhancing lesions and or T2/FLAIR is restricted to the initial radiation therapy volume.

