- There are no new enhancing lesions outside of the initial radiation therapy volume.
- Patients are stable or improved clinically.
- PsP may be diagnosed at any time during therapy (beyond the typical 12 week window defined by RANO).

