- 16.83 **Patterns of Failure:** observe patterns of failure after reirradiation using  $^{18}\text{F}$ -DOPA-PET to guide treatment volumes. The MRI scan indicating progressive disease will be fused with our treatment planning scan and the region of progression will be contoured by an investigator blinded to the GTV\_MRI, T2\_FLAIR\_NCET, GTV\_PET, PTV\_high, and isodose lines. A volumetric analysis will then be performed to define the doses delivered to the absolute and relative volume of the region where recurrence is defined.
- 16.84 **Adverse Events:** determine acute and late toxicity after radiotherapy treatment using  $^{18}\text{F}$ -DOPA-PET to delineate treatment volumes. The rate of acute and late treatment-related toxicities for recurrent high-grade glioma patients treated with  $^{18}\text{F}$ -DOPA-PET image-guided radiotherapy will be determined, with acute RT toxicities graded using Common Terminology Criteria for Adverse Events (CTCAE) version 4.0 (available at <http://ctep.cancer.gov>), and late toxicities reported using RTOG/EORTC late toxicity criteria.[39]
- 16.85 **Reoperation Rates:** determine the rate of reoperation for patients undergoing reirradiation for recurrent high-grade gliomas treated using  $^{18}\text{F}$ -DOPA-PET guided volumes. When available, pathologic information detailing the presence of necrosis and/or tumor progression will be recorded.
- 16.86 **Quality of Life:** estimate quality of life (QOL) after radiotherapy using  $^{18}\text{F}$ -DOPA-PET to establish treatment volumes. QOL will be evaluated using the MD Anderson Symptom Inventory Brain Tumor Module (MDASI-BT) and fatigue will be evaluated using the MD Anderson Brief Fatigue Inventory. These questionnaires will be administered at baseline and at each MRI evaluation up to 6 total evaluations to capture quality of life and correlate findings with clinical and radiographic progression. Analysis will include change percent from baseline using t-tests and generalized linear models to test for changes at each time point and non-zero slope.

16.9 **Data Safety Monitoring Plan**

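### Patterns of failure are scored only on scans called progressive, but only growth inside the RT volume can be called pseudoprogression, so under one of the plan's two progression rules location affects who is analysed

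*Combined protocol and SAP*

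**What the plan says.** Section 7.9 opens the location analysis with "For patients who recur, follow-up imaging at progression will be co-registered with pre-treatment imaging" and measures the part of the recurrence that "falls within the 95% isodose line of the PTV from the reirradiation plan". Sections 7.91 to 7.93 then grade each failure as central, in field, marginal or distant, relative in turn to the reirradiation isodose, the T1 contrast-enhancing volume and the PET volume. Section 16.83 names the image: "The MRI scan indicating progressive disease will be fused with our treatment planning scan". It has the region contoured blind to the target volumes and isodose lines.

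Section 11.415 sets the conditions for PsP, all of which must hold. The patient must not have worsened clinically, and any new enhancing lesion beyond the irradiated volume rules the label out. The condition on site reads "Progression of contrast enhancing lesions and or T2/FLAIR is restricted to the initial radiation therapy volume". As to timing, the section lifts the usual limit: "PsP may be diagnosed at any time during therapy (beyond the typical 12 week window defined by RANO".

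Two progression rules sit beside this. Section 11.414 and footnote 1 of 11.416 make any one criterion sufficient, including a new lesion. Footnote 2 of 11.416 reserves confirmed PD for cases that meet four conditions: more than 3 months post RT, radiologic progression on central review, clinical progression judged by the treating oncologist, and not classifiable as PsP. Anything short of that is Preliminary PD. Footnote 3 back-dates a later-confirmed PD to the Preliminary PD cycle.

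Neither 7.9 nor 16.83 says what happens to PsP or Preliminary PD that is never resolved, or whether the first suspicious scan or the confirming scan is contoured.

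**The concern.** Goal 2.32 asks where failures occur relative to the pre-treatment MRI and PET abnormalities. A table of locations answers that only if a failure's chance of entering the table does not depend on its location. Here it can. Growth inside the RT volume can be set aside as PsP while the patient is stable; growth outside it has no such route. Leaving out treatment effect that later resolves is correct. The difficulty is true in-field tumour that carries the label and is never reclassified on a scan.

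Such loss is plausible. Section 1.6 gives a median survival of 7 to 10 months after reirradiation, and the test schedule puts MRI typically every 2 to 3 months at the clinician's discretion, so a confirming scan may never be taken. Section 11.414 counts failure to return because of death or deterioration as progression, but that route leaves no progression scan to contour.

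An in-field share that reads low could be taken as better local control or, by the reasoning of 1.6, as more geographic miss. Either reading would mislead on goal 2.32.

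**Working it through.** The plan states no target, test or expected figure for patterns of failure, so there is nothing to reproduce. The check has two parts.

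**Which failures can be withheld from scoring**

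- *Any-criterion rule (11.414, footnote 1).* A new lesion outside the volume is progression and is scored. Growth inside the volume in a stable patient can be PsP and is not scored while that label stands. Entry depends on site.
- *Footnote 2.* A stable patient with out-of-volume growth also remains Preliminary PD until clinical progression. Clinical worsening ends PsP as well, so both sites wait largely on the same trigger.
- *Meaning of the initial volume.* Every patient has had earlier brain RT (3.14). If the word refers to the first course, growth that is marginal or distant to the reirradiation isodose may also be held as PsP.
- *Other classification axes.* The target is built from GTV_MRI and GTV_PET (7.52). If the two are combined as a union, growth in a PET-only part of the target is eligible for PsP yet distant under 7.92. Growth in an MRI-only part is eligible for PsP yet distant under 7.93. Holding such cases removes distant failures on those axes, so the direction there is not determined.

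**Size on the 7.91 axis**

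Inputs:
- s, the true in-field share: 0.60 to 0.70, from 1.6 ("60-70% recurrences were located in-field with the remainder located out of field"). In-field is taken here as central plus in field; 1.6 does not define how the cited series used the term.
- h, the fraction of true in-field failures never scored, and g, the same for out-of-field failures. The documents give neither, so all values are assumptions.

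Observed share = s(1−h) / [s(1−h) + (1−s)(1−g)].

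| s | h | g | Calculation | Observed share |
|---|---|---|---|---|
| 0.60 | 0.2 | 0 | 0.48 / (0.48 + 0.40) | 54.5% |
| 0.70 | 0.2 | 0 | 0.56 / (0.56 + 0.30) | 65.1% |
| 0.60 | 0.4 | 0 | 0.36 / (0.36 + 0.40) | 47.4% |
| 0.70 | 0.4 | 0 | 0.42 / (0.42 + 0.30) | 58.3% |
| 0.60 | 0.2 | 0.2 | 0.48 / (0.48 + 0.32) | 60.0% |
| 0.60 | 0.1 | 0.3 | 0.54 / (0.54 + 0.28) | 65.9% |

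The first four rows represent the any-criterion rule with no out-of-field loss. The fifth represents equal holding, as footnote 2 would tend to produce: the share does not move. The sixth shows the bias reversing when out-of-field loss is the larger.

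For scale, a shift of about 5 points is 0.05 × 20 = 1 patient in 20 failures. The exact 95% interval for 13 of 20 in-field failures is 40.8% to 84.6%.

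**The case against.** A reader might infer that in-field growth can be held indefinitely, that out-of-field growth counts at once, and that the bias therefore always runs downward. The documents do not support that.

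- *Indefinitely.* PsP requires clinical stability, so the label fails once the patient worsens. Many true in-field failures would then be scored later and back-dated. Section 1.3 describes pseudoprogression as enhancement that subsides. Footnote 3 has the current cycle recorded as SD, PR or CR if progression is not confirmed, and SD requires less than a 25% increase. That implies some test of resolution, although 11.415 states none and no deadline is given.
- *At once.* This holds under 11.414 and footnote 1 but not under footnote 2.
- *Always downward.* The formula gives this only because g is set to zero. The undefined initial volume and the 7.92 and 7.93 axes leave room for other directions.

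Nor can it be shown that PET-guided volumes will look better than the cited series. Section 16.83 only observes patterns, the goals that name historical controls are 2.11 and 2.21, and how those series handled pseudoprogression is not visible here. An informal comparison is still foreseeable, because one of the series behind the 60-70% figure is among the historical controls listed in 7.11.

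The shift is also small beside sampling error at this size. That is true, but a confidence interval does not account for selection. What stands is that no rule says how unresolved cases enter the analysis, and that under one of the plan's two progression rules entry depends on site.

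**Conclusion.** The concern holds in a limited form. Sections 7.9 and 16.83 condition on a progression call that, under 11.414 and footnote 1, depends partly on location. On the 7.91 axis the likely effect is an in-field share that reads low. With 20% of in-field failures never scored and no out-of-field loss, 60-70% would read about 55-65%; with 40%, about 47-58%. Both fractions are assumptions, as is the absence of out-of-field loss.

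Permanent loss is confined to patients who stay clinically stable until imaging ends (up to 2 years), who withdraw, or who die or deteriorate without a further scan. Their number cannot be derived from the documents. Under footnote 2 the asymmetry largely disappears, and for 7.92 and 7.93 no direction can be stated. The aim is correlative and descriptive in about 20 patients, and the primary endpoint's stated alpha and power are not part of this point. The change is still worth making because it is cheap and works whichever reading applies.

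**What to change.** - In 7.9 and 16.83, define the scan to be contoured as the first one meeting the radiologic criteria of 11.414 in every treated patient, whether its status is Preliminary PD, PD or PsP. Keep the blinded contouring that 16.83 already requires.
- Report the 7.91 to 7.93 classifications by final status: confirmed PD, unresolved Preliminary PD or PsP, and resolved PsP. Also state how many patients progressed with no scan to classify.
- Give the in-field share twice, with PsP and unresolved cases excluded and included, before any comparison with published series.
- State which RT course the initial volume in 11.415 refers to.
- Reconcile footnotes 1 and 2 of 11.416 and say which progression rule feeds this analysis.

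The cost is a wording change and contouring of a few extra MRIs that already exist, with no new imaging. The in-field share becomes a range instead of a single figure.

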### 2.3 Correlative Research

- 2.31 Compare volume of  $^{18}\text{F}$ -DOPA-PET uptake with MRI contrast enhancement and T2 FLAIR for patients undergoing re-irradiation for recurrent high-grade glioma
- 2.32 Evaluate patterns of failure after reirradiation in relation to pre-treatment MRI and  $^{18}\text{F}$ -DOPA-PET abnormalities

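### The MRI- and PET-based failure labels in 7.92 and 7.93 depend on shrinkage history and contour size as well as on where the tumour failed

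*Combined protocol and SAP*

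**What the plan says.** Section 7.9 sorts failures into four classes by the share of the recurrence volume (RecVol) inside a reference volume: above 95% is 'central', 80-95% 'in field', 20-80% 'marginal' and below 20% 'distant'. Section 7.91 uses the 95% isodose as the reference. Section 7.92 uses enhancement: "Failures will be documented as 'central' relative to the T1-CE MRI if >95% of the recurrence volume is within the T1-CE volume". Section 7.93 asks instead what share "of the recurrence volume is within the PET volume (defined as T/N > 2.0"). The cut-offs are the same throughout, and no margin is added to the T1-CE or PET contour.

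The recurrence is defined on MRI, since 7.71 says "Standard of care MRI scans will be used for follow-up imaging" and requires no further PET. Under 16.83, "the region of progression will be contoured by an investigator blinded to the" pre-treatment volumes and isodose lines. It does not say whether that region is the whole lesion or only the new growth.

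Size progression in 11.414 is a rise of at least 25%, measured as an "increase in the sum of products of perpendicular diameters of enhancing lesions compared to the smallest tumor measurement obtained" at baseline (if there was no decrease) or at best response. Other routes to progression are a new lesion, a T2/FLAIR increase and clinical decline.

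The labels serve correlative goal 2.32: "Evaluate patterns of failure after reirradiation in relation to pre-treatment MRI and" PET abnormalities.

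**The concern.** Cut-offs of 80% and 95% leave little room for a lesion to outgrow an unexpanded contour before it loses the 'central' or 'in field' label. Yet a lesion must grow to count as a size progression at all. A failure centred exactly on the original enhancing tumour can therefore be reported as 'marginal' only because it grew evenly past its old edge.

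Objective 2.32 asks where failures lie relative to each modality. If the label also reflects how far the lesion shrank beforehand and how large each contour was, the 7.92 and 7.93 labels cannot answer that question alone.

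**Working it through.** The documents give no figure for these classes, so there is nothing to reproduce first.

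**Inputs from the documents.** Cut-offs of 95/80/20% (7.92, 7.93); a 25% rise in the product of diameters from the smallest measurement (11.414).

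**Assumptions.** Spherical lesion, even concentric growth, whole lesion contoured.

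**Formula.** The product of diameters scales as D² and volume as D³, so a product ratio g gives a volume ratio g^1.5. The share of the recurrence inside the baseline contour is min(1, 1/g^1.5).

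**1. No earlier shrinkage.** With g = 1.25, the volume ratio is 1.25^1.5 = 1.3975 and the share is 1/1.3975 = 71.6%: 'marginal'.
- 'Central' needs g below (1/0.95)^(2/3) = 1.035, that is, growth under 3.5%.
- 'In field' needs g of at most (1/0.80)^(2/3) = 1.160, that is, growth of at most 16.0%.
- Both lie below the 25% threshold.

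The distance involved is small. A lesion 30 mm across (radius 15 mm) grows to a radius of 15 × √1.25 = 16.77 mm, or 1.77 mm outward. A margin of about 1.5 mm on the reference contour would bring the share to 95%.

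**2. Earlier shrinkage.** If the smallest product is a fraction f of baseline, progression occurs at g = 1.25f.
- The 80% boundary is at f = 1.160/1.25 = 0.928.
- The 95% boundary is at f = 1.035/1.25 = 0.828.

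| Earlier product decrease | Label at progression |
|---|---|
| under about 7% | marginal |
| about 7-17% | in field |
| over about 17% | central |

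From a 20% decrease onward the share is 100%, because 1.25 × 0.80 = 1.

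**3. PET label for the same recurrence as in step 1.** Let k be the PET:T1-CE volume ratio, concentric. The share inside PET is min(1, k/1.3975). The documents do not give k, so a range is assumed.

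| k | Share inside PET | PET label | T1-CE label |
|---|---|---|---|
| 0.75 | 53.7% | marginal | marginal |
| 1.0 | 71.6% | marginal | marginal |
| 1.2 | 85.9% | in field | marginal |
| above 1.33 | above 95% | central | marginal |

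The last boundary is 0.95 × 1.3975 = 1.328.

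**4. Displaced PET volume.** Take a 30 mm lesion and a PET volume twice the T1-CE volume, and apply the two-sphere overlap formula. The share inside PET is 91.8%, 78.8%, 69.8% and 48.4% at displacements of 5, 8, 10 and 15 mm, against 71.6% inside T1-CE. By 10 mm the larger volume no longer scores higher.

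**5. Meaning of RecVol.** If only the new rim in step 1 is contoured, the share inside T1-CE is 0%: 'distant'. The same failure thus moves from 'marginal' to 'distant' on a point that 16.83 leaves open.

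**The case against.** The strongest objection is that step 1 describes one scenario. Progression counts from the smallest measurement. The protocol states that "we recommend use of concurrent bevacizumab with radiotherapy when possible" (7.6), and section 1.5 describes rapid falls in enhancement after VEGF inhibitors as fairly common. Earlier shrinkage is therefore foreseeable, and many central regrowths may be labelled 'in field' or 'central'. This stands: a reader should not infer that every central regrowth will be called 'marginal'. It also shows that the label varies with shrinkage history at a fixed location.

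A reader might also infer that the larger contour always scores higher, or that the rule makes MRI look worse than PET. Neither is supported. The first holds for concentric or nested volumes and fails under enough displacement (step 4). PET uptake outside the MR volume is something the protocol expects and measures (7.4). The second would need the PET:T1-CE volume ratio; at 0.75, PET has the smaller share.

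Finally, the labels are descriptive, no test between the MRI and PET labels is planned, and at most 20 evaluable patients are expected. Section 16.83 also plans an analysis of dose to the recurrence, and 7.931 explores FLAIR, other T/N thresholds and SUV levels. This limits the stakes. It does not supply the missing location measure: the overlap and distance metrics in 7.4 and 16.82 compare pre-treatment volumes, not failures.

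**Conclusion.** The concern holds in limited form and is minor. The 7.92 and 7.93 labels mix location with growth since baseline and with the size of the reference contour. The 71.6% figure requires all of step 1's conditions: spherical shape, concentric three-dimensional growth, whole-lesion contouring, no earlier shrinkage, and progression at exactly 25%. Growth in two dimensions only would give 1/1.25 = 80%, which falls on the boundary shared by 'in field' and 'marginal'.

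The arithmetic does not apply to progression by a new remote lesion or by clinical decline, nor directly to a T2/FLAIR increase, for which 11.414 sets no percentage. The primary endpoint is unaffected.

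**What to change.** In 7.92, 7.93 and 16.83:

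- State that RecVol is the whole recurrent lesion, and report new growth outside the baseline contour separately.
- For each recurrence component, report whether its centroid lies inside the T1-CE, PET and FLAIR volumes and the 95% isodose, with the signed distance in mm to each surface.
- Report percent overlap as a continuous figure, together with the size of each reference volume.
- Keep the 95/80/20 labels, if wanted, for comparison with the literature, but do not rest the MRI-versus-PET conclusion for objective 2.32 on the 7.92 and 7.93 labels alone.

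In the concentric case the centroid lies inside both volumes, so both modalities get the same answer.

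The cost is a little more analysis, using contours and software already planned. Rim-shaped or multifocal recurrences need one centroid per component and cautious reading, because the centroid of a rim can lie inside the old volume while all the new disease is outside it. Signed distance still depends partly on contour size, which is why the reference volumes should be reported with it.
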